#### 1. Research Background

The human gut microbiota is one of the most abundant microbial communities on earth, containing highly diverse microbial communities that provide metabolic, immune, and protective functions and play a critical role in human health. The gastrointestinal microbiome is influenced by a variety of factors, including neural stress, genetics, host physiology (host age, disease, etc.), and environmental factors such as living conditions and drug use. At the same time, the vagus nerve (VN) is considered to be a key component of the autonomic nervous system (ANS), which innervates most of the digestive tract and many GI organs such as esophagus, stomach, small intestine, and colon. It also innervates important organs in the digestive system such as liver, pancreas, and gallbladder. The vagus nerve transmits excitation to the corresponding brain regions by sensing stimulation in the intestine, and regulates the gut and brain bi-directionally through the "gut-brain axis".

Recent studies have shown that VN has anti-inflammatory effects. This vagal function is mediated through a variety of pathways, some of which are still controversial. The first is the anti-inflammatory pathway of the hypothalamic-pituitary-adrenal axis, stimulated by the afferent fibers of the vagus nerve, where the adrenal gland releases cortisol, providing an important first line of innate defense against inflammatory infections and helping to restore homeostasis. The second, called cholinergic anti-inflammatory pathway, releases acetylcholine (ACh) at synaptic junctions with macrophages through synaptic connections of enteric neurons mediated by vagal efferent fibers. Acetylcholine binds to the  $\alpha$ -7-nicotinic acetylcholine receptor of macrophages and inhibits the release of tumor necrosis (TNF) $\alpha$ , a proinflammatory cytokine. The last pathway is the splenic sympathetic anti-inflammatory pathway, where stimulation of splenic sympathetic nerves by VN leads to the distal release of acetylcholine by norepinephrine (noradrenaline). Finally, ACh inhibits TNF $\alpha$  release from splenic macrophages via  $\alpha$ -7-nicotinic ACh receptors.

Irritable bowel syndrome (IBS) is a highly prevalent functional digestive disorder characterized by chronic abdominal pain and altered bowel habits in the absence of biological or structural abnormalities. In the field of IBS, effective medical treatments are very limited, and

patients are urgently looking for alternatives, including probiotics, hypnotherapy, osteopathic therapy, dietary changes, and fecal microbiota transplantation. In recent years, with the continuous elucidation of the vagus nerve mechanism, IBS patients have become more and more interested in bioelectrical modulation. These patients are usually skeptical of traditional drug treatment and believe that drugs are easy to cause side effects. For the above reasons, vagus nerve stimulation (VNS) may be a promising option for improving IBS symptoms.

In fact, the interaction between the gut and nervous system seems to be one of the links of the brain-gut axis, which is mainly regulated by the autonomic nervous system. The anti-inflammatory effect of VNS has been demonstrated in previous studies, while low-grade intestinal mucosal inflammation has been reported in IBS. In the gut, the vagus nerve is also the interface for the interaction between the microbiota and the mucointestinal tract, suggesting that there may be dysbiosis in VN in IBS.

Vagus nerve stimulation (VNS) is currently used as a treatment option for many clinical conditions, such as heart failure, migraine, and inflammatory bowel disease. VNS techniques are mainly divided into invasive (surgical implantation) and noninvasive (percutaneous)VNS techniques. Invasive VNS (iVNS) involves implantation of a programmable pulse generator device in the chest wall and placement of electrodes around the left (typical) cervical vagus nerve. As it stands, iVNS carries several potential risks, such as bradycardia and cardiac arrest, localized infection around the wound, etc. The transcutaneous VNS (tVNS) delivery system relies on the skin distribution of the vagal afferent nerve and intervenes in the external ear (auricular branch of the vagus nerve) or neck (cervical branch of the vagus nerve), which avoids the risk of surgical implantation of VNS delivery devices and promotes further research on the application of tVNS.

In this study, the portable conchal stimulator produced by Ruizhenan Medical can accurately stimulate the conchal boat and stimulate the auricular vagus nerve percutaneously, giving full play to its therapeutic effect. Therefore, the purpose of this clinical trial is to use the conchial stimulator in patients with irritable bowel syndrome, and to explore whether it has a therapeutic effect on patients with irritable bowel syndrome. To explore the effect of tVNS therapy on irritable bowel syndrome (IBS) compared with drug therapy, hoping that the use of TVNS therapy can reduce the use of related drugs, or even replace drugs.

Ruisen auricular concha vagus nerve stimulator can be used directly without installation. It is easy to carry and can be turned on at any time, without affecting daily work and life (as shown below). The current approved indications are as follows: for sleep disorders, anxiety, loss of appetite, fatigue as an adjunct treatment, and diabetes as an adjunct treatment. In foreign countries, concha vagus nerve stimulation has been approved for the adjuvant treatment of epilepsy and depression. At present, some hospitals in China have introduced new technologies for the treatment of disorders of consciousness, stroke rehabilitation, migraine, epilepsy, pain intervention and so on.

Schematic illustration of the actual use of the auricular concha stimulator by the participants

According to Mion, F et al. (2020), transcutaneous auricular stimulation of the left vagus nerve (taVNS) has been shown to improve symptoms of irritable bowel syndrome (IBS). In 12 patients with IBS, taVNS was applied for 6 months for at least 3 hours per day (preferably before bedtime), 5 days per week, with continuous stimulation at a pulse width of 250  $\mu$ s and a frequency of 30 Hz. Results Effective data were obtained in 9 patients (4 with diarrhea type and 5 with constipation type). IBS-SSS was significantly decreased at 3 and 6 months (baseline: 336, 3 months: 231[p = 0.0084]; The IBS-SSS decreased from 336 at baseline to 231 at 3 months [p = 0.0084], and 246 at 6 months [p = 0.0209].

According to the above research results, combined with the characteristics of the auricular

conchae stimulator that is portable and does not affect daily life and work, this study aims to use auricular conchae stimulation with pulse width of 200µs, frequency of 30Hz, 3 hours a day for 8 weeks to improve the clinical symptoms of patients with irritable bowel syndrome.

#### 2. Objectives of the study

This study aimed to recruit a group of patients with irritable bowel syndrome (IBS) to use the Ruisenan portable auricular conic stimulator. (1) To observe the improvement of symptoms in patients with IBS; (2) To analyze the changes of gut microbiota in patients with irritable bowel syndrome; (3) verify whether the level of intestinal inflammation is reduced and find metabolic markers in the gut.

#### 3. Study design

This was a randomized, double-blind study without placebo. Forty patients with physician-diagnosed IBS-D were recruited. The recruited patients were randomly assigned to undergo either real tVNS (transcutaneous vagus nerve stimulation) or sham TVNS (using the same device but without vagus nerve stimulation) at different times.

#### 4.Selection of subjects

#### 1. Eligibility Criteria

1.1 Patients with colorectal cancer were excluded by colonoscopy within two years, and the clinical manifestations were diarrhea predominant irritable bowel syndrome, which met the Rome IV diagnostic criteria. That is, recurrent abdominal pain or discomfort, occurring at least 3 days per month in the past 3 months, and meeting the following two or more points:

- (1) Improvement after defecation;
- (2) the change of the frequency of defecation;
- (3) The onset of the disease accompanied by changes in stool character (appearance).

\* Symptoms have been present for at least 6 months before diagnosis, and symptoms have met the above criteria for the past 3 months

\* Discomfort refers to non-painful discomfort. For pathophysiological studies and clinical trials, the frequency of pain/discomfort used for screening assessment is at least two days per week when selecting subjects for research.

1.2 Patients with diarrhea and irritable bowel were mainly selected for enrollment.

1.3 The enrolled patients with IBS were between 18 and 65 years of age and had a normal electrocardiogram before enrollment.

1.4 Subjects were excluded from the study if they did not meet the requirements by having them fill out the questionnaire to assess the health status of the intestinal health-related questionnaire.

#### 2. Exclusion criteria

[figure not shown]
(a) patients with other gastrointestinal diseases; (b) patients with a history of previous abdominal surgery, cardiovascular disease or serious illness; (c) in the past month, the participant has used medications that could affect the outcome of the study (e.g., probiotics, prebiotics, antibiotics, laxatives, prokinetic drugs); (d) pregnant women; And (e) patients enrolled in other clinical studies.

#### 5. Estimation of sample size

Forty patients with diarrhea-predominant irritable bowel syndrome

[figure not shown]
#### **6.Study PROCEDURE**

Stool samples were collected from patients with diarrhea-type irritable bowel syndrome. The auricular concha-stimulator was used for 3 hours per day with a pulse width of 200µs and a frequency of 30Hz. Each patient was randomly selected for true stimulation or sham stimulation every 4 weeks for 8 weeks, resulting in a total of 4 groups, namely, true-true, true-false, false-true, and false-false (FIG. 2). Stool samples were collected on day 0, day 28 and day 56. Stool samples were collected two weeks after the end of the treatment. Patients completed questionnaires on day 0 and every other 7 days thereafter, for a total of 11 questionnaire collections (Figure 1); the questionnaires are shown in Table 2.

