#### Figure 2 Schematic representation of patient randomization

A questionnaire was used to determine whether the symptoms of patients with irritable bowel syndrome improved, and stool samples were collected on days 0, 28, 56, 63, and 70 for 16s sequencing analysis. To study the changes in intestinal microbial composition and intestinal marker metabolites in patients before and after the intervention of ear conchal stimulator. Continuous sampling survey was conducted 2 weeks after treatment to observe the long-term effect of tVNS treatment, and to explore whether the irritable bowel level of patients would return to the level before treatment or could be improved after stopping the stimulation.

The study did not require recruitment advertisement, and the recruitment of subjects was completely voluntary. The possible risks in the process of the study were explained to the subjects, and the subjects signed the informed consent form after they agreed to participate in the study. A questionnaire survey was conducted on the volunteers who agreed to participate in the study to obtain their intestinal health and other health status. The subjects were screened according to the above selection criteria and exclusion criteria. The collected samples were named by number, and no personal information of the subjects was disclosed. The identity of the subjects was kept confidential throughout the study, only the number and disease phenotype were visible. Subjects may withdraw from the study at any time stage.

The composition and structure of gut microbiota of the subjects will be analyzed. Subjects can keep informed of the progress of the experiment and analysis and obtain their own relevant data at any time.

The auricular conchal stimulator used in this study was manufactured by Ruisenan Medical Company. The portable conchal stimulator used in this study was in the form of earphones, which was well accepted by patients. It is easy to use and can be used at night before going to bed without affecting the normal life of the participants. The contact point of the earphone was closely fitted to the left ear conchial boat, which precisely stimulated the conchial boat and gave full play to the therapeutic effect. The instrument has three optional modes to meet the needs of personalized treatment.

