#### 8. Possible risks and preventive measures

#### 1. Possible risks:

① During the study period, if the patient's skin is allergic to the ear electrode, the use of the ear electrode can be immediately suspended, and the stopping date and time can be recorded.

② If the current density of the electrode exceeds 2mA(r.m. s)/cm2, special attention should be paid to the use of the electrode. In case of discomfort, please stop using the electrode immediately or reduce the pulse amplitude.

2. Preventive measures:

If the symptoms of patients are not improved significantly after receiving otovagus nerve stimulation, the researchers of this experiment, as digestive specialists, will give further professional guidance, including drugs, psychological counseling, traditional Chinese medicine and other comprehensive programs, in order to improve the symptoms of patients.

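### Skin allergy and discomfort are named as device risks, but the weekly forms shown ask about neither and no safety outcome is planned, so non-bowel harms and stimulation changes cannot be compared reliably between true and sham periods

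*Combined protocol and SAP*

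**What the plan says.** **Collection schedule (Section 6).** "Patients completed questionnaires on day 0 and every other 7 days thereafter, for a total of 11 questionnaire collections". The text under the Figure 2 caption gives the purpose of the questionnaire as judging whether IBS symptoms improve. It sets the last stool sample at day 70: "stool samples were collected on days 0, 28, 56, 63, and 70 for 16s sequencing analysis".

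**Forms (after the references).** Table 1 is the 13-item GSRS-IBS. An untitled second scale, probably the Table 2 that Section 6 refers to, has 34 items on bowel-related quality of life.

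**Device risks (Section 8).** For skin allergy, "the use of the ear electrode can be immediately suspended, and the stopping date and time can be recorded". The next item concerns current density and ends "In case of discomfort, please stop using the electrode immediately or reduce the pulse amplitude", with nothing on recording. The preventive-measures paragraph deals with patients whose symptoms do not improve, not with either listed risk.

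**Analysis (Section 9).** The outcomes are pain, diarrhea frequency, distension and GSRS-IBS severity, with microbiota correlations. No safety outcome or tabulation of harms is described.

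**Cardiac status.** Section 1 says that "iVNS carries several potential risks, such as bradycardia and cardiac" arrest, where iVNS means the implanted device. Section 4 requires that patients "had a normal electrocardiogram before enrollment" and excludes cardiovascular disease. No later cardiac question or check is described.

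**Design (Sections 5 and 6).** "Forty patients with diarrhea-predominant irritable bowel syndrome" are randomized over two 4-week periods, "resulting in a total of 4 groups, namely, true-true, true-false, false-true, and false-false".

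**The concern.** The plan names two ways in which the device may trouble a patient and has patients complete forms every week, but the forms shown ask about neither. A patient with a sore ear, electrode pain or dizziness enters the data only by volunteering it, and the plan does not say where such a report would go.

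Two things are at stake. The first is tolerability: harm data that are not collected during the trial cannot be recovered at analysis, and an absence of reports could not be read as an absence of harm. The second is the efficacy comparison. The output level is adjustable (Section 7), and Section 8 lets patients stop or turn it down for discomfort. An unrecorded stop or reduction hides a change in the stimulation received, which may differ between true and sham periods and affects how the symptom difference is read.

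**Working it through.** **1. The plan's own count.** Days 0, 7, ..., 70 give 70/7 + 1 = 11 collections, which matches Section 6. Reading the interval as 14 days would give 70/14 + 1 = 6, so weekly is the reading that fits. Four collections fall in period 1 (days 7, 14, 21, 28), four in period 2 (days 35, 42, 49, 56) and two after treatment (days 63, 70). A harms question on this schedule would ascertain true and sham periods equally.

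**2. Named risks against recording.**

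| Event | Asked on the forms shown? | Recorded under Section 8? | Analysed under Section 9? |
|---|---|---|---|
| Skin allergy leading to a stop | No | Stop date and time, permissively worded | No |
| Stop for discomfort | No | No | No |
| Amplitude reduction for discomfort | No | No | No |
| Other non-bowel symptom | No | No | No |
| Worse pain, diarrhea or bloating | Yes, every form | Not applicable | Yes, as efficacy |

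Of the 13 + 34 = 47 items, 0 concern a non-bowel harm.

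**3. Who is exposed.** No allocation ratio is stated. Assuming 10 patients per sequence, true stimulation is received by true-true, true-false and false-true: 10 + 10 + 10 = 30 patients. Scheduled device use is 3 h x 56 days = 168 h per patient. Scheduled true stimulation is 168 h in true-true, 3 x 28 = 84 h in each mixed sequence, and none in false-false.

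**4. What solicited capture could show.** The documents give no event rates, so the risks below are assumptions. The chance of at least one case is 1 - (1 - p)^n. The one-sided 95% upper bound after zero cases is 1 - 0.05^(1/n).

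| n | p = 1% | p = 5% | p = 10% | Bound if zero cases |
|---|---|---|---|---|
| 20 (true in period 1 only) | 18.2% | 64.2% | 87.8% | 13.9% |
| 30 (any true stimulation) | 26.0% | 78.5% | 95.8% | 9.5% |

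For n = 30 and p = 5%: 1 - 0.95^30 = 0.785. For zero cases: 1 - 0.05^(1/30) = 0.095. Using all 40 patients would give 87.1% and 7.2%, but that counts the false-false group, which never receives true stimulation.

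**5. What it could not show.** With 20 true and 20 sham patients in period 1 (equal allocation again), the power of a two-sided 5% test of two proportions (normal approximation) is 29% for 5% against 20%, and 55% for 5% against 30%. A harms table in this trial is descriptive.

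**The case against.** **Removed text may say more.** Figures, consent pages and some other pages were not available, and Section 6 says that risks were explained before consent. This limits the point to the readable text. But Sections 6, 8 and 9, where collection and analysis would be set out, are readable and contain none. Explaining a risk does not collect data on it, and the survey of general health in Section 6 belongs to screening.

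**The permissive wording may be a translation artefact.** That is plausible, and the point does not depend on it. The stronger evidence is that discomfort has no record at all and that Section 9 has no safety outcome.

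**A reader might infer that the device carries a named cardiac risk that goes unmonitored.** The documents do not support this. Bradycardia and cardiac arrest are attributed to implanted stimulation, and Section 8 lists no cardiac risk for this device. What stands is that ECG and cardiovascular history are screened at entry, with no later cardiac question described.

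**A reader might infer that no harms can be compared.** That is too broad. Worsening of pain, diarrhea, bloating and bowel-related quality of life is asked about on both scales throughout.

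**A reader might infer that spontaneous reports are bound to differ because true stimulation is felt and sham is not.** Section 3 says only that sham uses the same device without vagus nerve stimulation, not what patients feel. Uneven reporting is a reasonable worry, not a documented fact.

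**Asking may unblind.** Weekly questions on electrode sensation and amplitude could prompt patients who switch condition, or staff who read the answers, to guess the condition. This stands, and it governs where the checklist is placed and who sees it.

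**Conclusion.** The point holds in limited form. On the readable text, two device risks are named, one has a loosely worded record of stops and the other has none. None of the 47 items shown asks about a non-bowel harm, and no safety outcome is planned. Non-bowel harms and stimulation changes in true and sham periods therefore cannot be compared reliably.

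In size, the loss is the ability to interpret a low or zero count. Under equal allocation, complete solicited capture in the 30 patients ever given true stimulation would let a zero count bound the risk at 9.5%; unsolicited reports give no such bound. The 78.5% and 9.5% rest on equal allocation, no dropout and complete reporting, and the 78.5% also on an assumed 5% risk. The finding itself rests on none of these. The gap should be closed before the trial runs, because it cannot be repaired at analysis.

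**What to change.** 1. At each of the 11 collections, add a short checklist, worded identically for true and sham and completed after the GSRS-IBS and quality-of-life scales. Items: ear-skin reaction; pain or discomfort at the electrode; dizziness or fainting; palpitations; any stop or amplitude reduction since the last form, with date and reason; any other new symptom.
2. In Section 8, make the recording of stops mandatory, and extend it to stops and amplitude reductions for discomfort. This changes what is recorded, not when a patient stops or reduces.
3. In Section 9, add one descriptive table of harms, stops and reductions by condition received in each 4-week period and in days 57-70, with the number of patients exposed as the denominator.
4. Keep the checklist on a separate sheet, away from those who assess symptom outcomes.

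Cost: about six items on forms already collected, one table and a minor amendment, with no new visit or test. The forms become slightly longer. Solicited event rates will look higher than spontaneous ones. A small risk remains that the questions prompt patients or staff to guess the condition, which steps 1 and 4 reduce but do not remove.

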**Collection of stool samples** 

FIG. 1 Experimental design time schedule

#### Figure 2 Schematic representation of patient randomization

A questionnaire was used to determine whether the symptoms of patients with irritable bowel syndrome improved, and stool samples were collected on days 0, 28, 56, 63, and 70 for 16s sequencing analysis. To study the changes in intestinal microbial composition and intestinal marker metabolites in patients before and after the intervention of ear conchal stimulator. Continuous sampling survey was conducted 2 weeks after treatment to observe the long-term effect of tVNS treatment, and to explore whether the irritable bowel level of patients would return to the level before treatment or could be improved after stopping the stimulation.

The study did not require recruitment advertisement, and the recruitment of subjects was completely voluntary. The possible risks in the process of the study were explained to the subjects, and the subjects signed the informed consent form after they agreed to participate in the study. A questionnaire survey was conducted on the volunteers who agreed to participate in the study to obtain their intestinal health and other health status. The subjects were screened according to the above selection criteria and exclusion criteria. The collected samples were named by number, and no personal information of the subjects was disclosed. The identity of the subjects was kept confidential throughout the study, only the number and disease phenotype were visible. Subjects may withdraw from the study at any time stage.

The composition and structure of gut microbiota of the subjects will be analyzed. Subjects can keep informed of the progress of the experiment and analysis and obtain their own relevant data at any time.

The auricular conchal stimulator used in this study was manufactured by Ruisenan Medical Company. The portable conchal stimulator used in this study was in the form of earphones, which was well accepted by patients. It is easy to use and can be used at night before going to bed without affecting the normal life of the participants. The contact point of the earphone was closely fitted to the left ear conchial boat, which precisely stimulated the conchial boat and gave full play to the therapeutic effect. The instrument has three optional modes to meet the needs of personalized treatment.

The medical device registration certificate number of Ruisenan portable ear conchial stimulator is 20212090050, which meets the national standards for medical devices. The range (level) of Ruisenan portable auricular concha stimulator is 1-60; Frequency (Hz) range: 1-120; Pulse width ( $\mu$ s) range: 100, 200; Pulse on (off) time (s) range: 10-200. A variety of diseases can be treated by parameter adjustment, such as: sleep disorders, anxiety, depression, fatigue, pain, tinnitus, rehabilitation and so on.

Product design diagram:

The product inspection certificate is shown in Annex 1.

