#### 9. Data collection and statistical analysis

The degree of pain, the frequency of diarrhea, and the degree of abdominal distension were used to evaluate the changes in the patient's irritable bowel status. The degree of pain refers to the use of psychometric practices to evaluate the patient's subjective feeling, which is also considered to be the main factor to evaluate the poor health-related quality of life (HRQL). The severity of irritable bowel syndrome was measured according to the Gastrointestinal Symptom Rating Scale for Irritable Bowel Syndrome (GSRS-IBS). On the GSRS-IBS scale, a score of 1 to 3 is defined as mild symptoms, a score of 4 or 5 as more severe, and a score of 6 or 7 as extremely severe.

Two-way analysis of variance (ANOVA) was used for statistical analysis. Two-sided t test was used for pairwise comparison, and p value was corrected for multiple comparisons. Kruskal-Wallis test was used for multiple group comparison. Spearman correlation analysis was used to determine the correlation between gut microbiota alterations and biological and pathological parameters related to constipation, with p values corrected by Benjamini-Hochberg method (Benjamini and Hochberg, 1995). A False Discovery Rate (FDR) threshold of 0.1 was used to consider the p value statistically significant. p < 0.05 or p < 0.01 was considered statistically significant. All rule plots were generated using GraphPad Prism version 8.0 (La Jolla, CA, United States). All statistical analyses were performed using GraphPad prismore and R(version 4.1.2,https://www.r-project.org/)

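### Persistence is called long-term on two weeks off treatment and judged against each patient's own baseline, while the sham-controlled sequence contrasts that could test it are not pre-specified

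*Combined protocol and SAP*

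**What the plan says.** Section 6 gives the design: "Each patient was randomly selected for true stimulation or sham stimulation every 4 weeks", "resulting in a total of 4 groups, namely, true-true, true-false, false-true, and false-false". Two four-week periods follow one another, and no washout is described. On measurement it says: "Patients completed questionnaires on day 0 and every other 7 days thereafter, for a total of 11 questionnaire collections". The text under Figure 2 adds that "stool samples were collected on days 0, 28, 56, 63, and 70 for 16s sequencing analysis".

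The persistence aim is in the same text: "Continuous sampling survey was conducted 2 weeks after treatment to observe the long-term effect of tVNS treatment". The question put to those data is "whether the irritable bowel level of patients would return to the level before treatment or could be improved after stopping the stimulation". No comparison group is named for it.

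Section 9 states: "Two-way analysis of variance (ANOVA) was used for statistical analysis". It adds corrected two-sided t tests for pairs and Kruskal-Wallis for several groups. It does not name the ANOVA factors, the pairs, a period or first-period-treatment term, or a measure of persistence.

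Two questionnaires are printed after the references. The GSRS-IBS asks about the previous two weeks. The 34-item bowel-problem form asks about the previous week.

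**The concern.** Comparing each patient's follow-up score with that patient's own baseline is an uncontrolled comparison. Section 4 admits patients because they have current symptoms, with a minimum number of symptomatic days per week for trial screening. Scores chosen for being high tend to fall on re-measurement whatever the treatment. Patients in false-false can therefore also end below baseline at day 70, and the before-after reading would count that as a lasting benefit in the treated sequences.

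The label compounds this. Readers will take long-term to mean more than two weeks.

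The design holds a better answer. In true-false, real stimulation stops at day 28 while the patient continues on the sham device, beside a concurrent randomised false-false group. Because the plan does not name that contrast, whether and how it is reported would be decided after the data are seen. The treatment comparison has a similar gap: with no washout and no stated rule for first-period treatment, different readings of Section 9 give different answers if any effect persists.

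**Working it through.** **Timeline.** Weekly forms from day 0 to day 70 number 70/7 + 1 = 11, which reproduces the plan's count. Real stimulation ends at day 56 in true-true (TT) and false-true (FT), and at day 28 in true-false (TF). At day 70 the time off is 70 − 56 = 14 days for TT and FT, and 70 − 28 = 42 days for TF. False-false (FF) never has real stimulation.

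**Forms whose recall lies wholly off real stimulation.**

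| Form | TT and FT, after day 56 | TF, after day 28 |
|---|---|---|
| GSRS-IBS, 2-week recall | 1 (day 70; the day-63 form covers days 49–63) | 5 (days 42, 49, 56, 63, 70) |
| 34-item form, 1-week recall | 2 (days 63, 70) | 6 (days 35 to 70) |

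Stool samples have no recall window. For TF, those on days 56, 63 and 70 are 4, 5 and 6 weeks off.

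**Carry-over.** Let τ be the treatment effect, λ an additive carry-over from period 1 into period 2, and π the period effect. Period-2 means, apart from π, are TT = τ + λ, TF = λ, FT = τ, FF = 0.

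- Pooled period 2, equal sequences: (TT + FT)/2 − (TF + FF)/2 = (τ + λ/2) − λ/2 = τ. No bias.
- TT − TF = τ and FT − FF = τ. No bias.
- FT − TF = τ − λ.
- TT − FF, if read as a period-2 effect, = τ + λ.
- Within-patient true versus sham: the changes from period 1 to period 2 are TF = π + λ − τ, FT = π + τ, TT = π + λ, FF = π. Regressing them on the change in treatment (−1, +1, 0, 0) gives [(π + τ) − (π + λ − τ)]/2 = τ − λ/2.

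At λ = 0.5τ these give 1.00τ (pooled), 0.50τ (FT − TF), 1.50τ (TT − FF) and 0.75τ (within-patient). At λ = τ the within-patient figure is 0.50τ.

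The pooled result depends on balance. With sequences of 12/8/8/12 or 8/12/12/8 (TT/TF/FT/FF) and λ = 0.5τ it moves to 1.10τ or 0.90τ. If carry-over is not additive, for example because improvement has a ceiling, it averages two different period-2 effects.

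Adding a first-period-treatment term to the within-patient model restores τ. The cost is precision. With 10 per sequence, the sum of squares carrying the treatment estimate falls from 20 (10 TF + 10 FT, each coded ±1) to 40 × 0.25 = 10, so the variance doubles.

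**Precision.** Section 5 gives "Forty patients with diarrhea-predominant irritable bowel syndrome" and no allocation ratio, so 10 per sequence is an assumption, as is no dropout. At two-sided 5% and 80% power with one score per patient, the normal approximation is (1.960 + 0.842) × √(2/10) = 1.25 SD, and the t-based value is 1.32 SD.

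- Power (t) is 19%, 40% and 56% at true differences of 0.5, 0.8 and 1.0 SD.
- Baseline adjustment multiplies the detectable difference by about √(1 − r²): 1.26, 1.15 and 0.95 SD at assumed r = 0.3, 0.5 and 0.7.
- Averaging five forms multiplies it by √[(1 + 4ρ)/5]: 1.03 and 1.16 SD at assumed between-form correlation ρ = 0.5 and 0.7, before baseline adjustment.
- As one of six group pairs under Bonferroni (an assumption, since the correction for the t tests is not named), it rises to 1.73 SD.
- Period 1, about 20 against 20: 0.89 SD (normal) or 0.91 SD (t).

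**The case against.** Several stronger readings are tempting, and the documents do not support them.

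- *The true-false against false-false comparison goes unused.* Section 9 plans corrected pairwise tests and Section 6 defines four groups, so this is one of the six possible pairs. It is not pre-specified, which is a smaller fault.
- *Persistence biases period 2.* Not in general. The four-sequence layout balances additive carry-over, and the pooled period-2 comparison is unbiased with equal sequences. Shrinkage to τ − λ/2 belongs to a within-patient model that Section 9 does not name. An ANOVA by group and time is at least as natural a reading.
- *The plan expects effects to persist.* It sets out to explore whether they do.
- *Only one form is wholly off treatment in the plan's window.* That holds for the GSRS-IBS in TT and FT. On the one-week form there are two.

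It is also fair to say that true-false against false-false answers a different question from the plan's. It measures persistence after four weeks of real stimulation followed by four of sham, not after the full eight weeks, so it complements the day-70 contrast and cannot replace it. The aim is exploratory and the groups are small.

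What stands is the label, the uncontrolled before-after reading, and the absence of a named controlled contrast or a stated rule for first-period treatment.

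**Conclusion.** The point holds in this limited form. The persistence aim rests on at most two weeks off treatment and on a comparison with baseline that cannot tell a lasting effect from regression to the mean or natural change. Randomised contrasts that can do so are already in the schedule, reaching 42 days off real stimulation, but are not pre-specified.

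The carry-over risk is conditional on the estimator. At λ = 0.5τ, analyses compatible with Section 9 range from 0.50 to 1.50 of the true effect, while the pooled period-2 comparison gives 1.00. These figures assume additive carry-over and equal sequences. The 1.3 SD detectable difference assumes 10 against 10, no dropout and a single score. This merits correction before analysis. It does not undermine the design.

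**What to change.** 1. In Section 6, replace the long-term wording with: effect up to 2 weeks after stopping.
2. In Section 9, define persistence as baseline-adjusted differences between randomised sequences: true-true minus false-false at day 70 and, as a complement, true-false minus false-false over the GSRS-IBS forms of days 42 to 70 and the stool samples of days 56, 63 and 70. Report estimates with intervals.
3. Name the period-1 comparison of true with sham as the main treatment estimate, since it is free of carry-over. Use the GSRS-IBS forms of days 14, 21 and 28, whose recall lies wholly within treatment; the day-7 form reaches back before day 0.
4. If a within-patient true-versus-sham model is also reported, include a first-period-treatment term and use period-2 GSRS-IBS forms from day 42, because the day-35 form still covers period 1. Accept the wider interval. The pooled period-2 comparison over four equal sequences does not need the term to remove additive carry-over.

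The cost is wording and analysis specification only: no new visits, patients or samples. The persistence claim becomes more modest, and its intervals will be wide.
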